### **5.3.3 Dosing day exclusion criteria**

Participants who at the time of randomization on Day 1 (i.e., pre-dose) meet one of the following criteria must not be dosed with the trial drug and should not be randomized but will be considered screening failures:

- If, in the investigator's medical judgment, further participation would be injurious to the participant's health or well-being.
- AEs or laboratory abnormalities occurring that in the opinion of the investigator may constitute a potential risk for continued participation by the participant.
- Major protocol deviation as discussed and agreed upon between the sponsor and investigator.
- The participant withdraws consent to participate.

### **5.4 Premature discontinuation of participants or trial**

#### **5.4.1 Participant discontinuation**

Participants will be informed that they have the right to withdraw from the trial at any time for any reason, without prejudice to their medical care. Participants who withdraw their consent prior to dosing will not receive any AEF0117. Participants who withdraw their consent after dosing will be offered all follow-up safety assessments.

The investigator also has the right to withdraw participants from the trial for any of the following reasons:

- Participant non-adherence to trial drug or protocol requirements.
- Participant unwillingness to continue in the trial.
- Medical judgment of the investigator.

If a participant is noncompliant in the opinion of the investigator, the sponsor should be consulted for instruction on handling the participant. If a participant is withdrawn from the trial, the trial monitor and the sponsor's clinical trial manager must be notified with 24 hours.

All participants must be followed for safety until the time of the follow-up evaluation or until trial drug-related toxicities resolve, return to baseline, or are deemed irreversible, whichever is longer. Participants who are discontinued from the trial prior to completion, regardless of reason, should have the assessments planned for the follow-up visit/early termination visit (see section 8.1.6) performed at the time of discontinuation. Reasonable efforts should be made to have the participant return for an early termination visit.

The date of discontinuation and the specific reason for discontinuation, such as withdrawn due to AE, will be recorded in the eCRF. This information will be used to summarize the reasons for trial discontinuation.

## **Participant withdrawal of consent**

If a participant withdraws his/her consent, no further data will be obtained. However, already recorded data may be used and obtained samples may be analyzed. This will be described in the ICF.

### **5.4.2 Treatment discontinuation**

In this trial, the 2 randomized groups may be divided into smaller cohorts of minimum 2 participants that are dosed sequentially for operational reasons. Administration of trial drug to participants scheduled to be dosed should be discontinued, at least temporarily, until a thorough evaluation of safety and relationship to trial drug has been performed, for any of the following reasons:

- Trial drug-related SAE in 1 participant in a cohort, or 2 or more trial drug-related SAEs of the same character across cohorts.
- Trial drug-related severe AE in 1 participant and AEs of the same character but less severe in the other participants in a dosing cohort (or severe AEs of the same character in one third of participants across at least 3 cohorts).
- Findings that, at the discretion of the investigator and/or sponsor, indicate that trial drug administration should be discontinued.

In case of unresolved relationship to trial drug for SAEs or severe AE in 1 participant and AEs of the same character but less severe in the other participants in a cohort (or SAEs of the same character across cohorts, or severe AEs of the same character in one third of participants across at least 3 cohorts), the trial may be temporarily interrupted/further dosing postponed. Except in cases of emergency, it is recommended that the investigator consult with the sponsor medical monitor (or other representative of the sponsor) before temporarily interrupting the trial. The investigator must obtain approval from the sponsor medical monitor before restarting dosing of the next cohort.

All patients who have been dosed with AEF0117 will be encouraged to continue to attend trial center visits through the 2-week post treatment follow-up visit to have safety assessments performed as scheduled.

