## 2.3 Risk-benefit assessment

### 2.3.1 Known and expected potential risks

This protocol represents an early trial of AEF0117 that will be conducted in parallel with an ongoing phase 2b trial; therefore, the long-term risks and benefits in humans are unknown. Safety data from preclinical studies with AEF0117 do not give rise to safety concerns, details can be found in the investigator's brochure [9].

In phase 1 single and multiple ascending dose studies in healthy volunteers, doses in the range of 0.2 to 6 mg were investigated. In total, 18 volunteers received doses of 0.6, 2, or 6 mg once daily for 7 days, and 30 volunteers received single doses of 0.2, 0.6, 2, or 6 mg. There were no SAEs reported in the 2 studies. AEF0117 was considered safe and with a limited number of mild TEAEs (except 2 TEAEs which were moderate) not related to the dose of AEF0117. There were only 2 noticeable TEAEs in 2 different participants. One participant in AEF0117-101 who received the single administration of 2 mg of AEF0117 showed an increase in creatine phosphate kinase (CPK) and myoglobin. One participant in AEF0117-102 developed a skin rash 30 minutes after the first administration of 0.6 mg of AEF0117 and was withdrawn from the trial.

In study AEF0117-201, 26 cannabis users, 0.06 and 1.0 mg AEF0117 was given once daily for 5 days and was also well tolerated.

Because this drug is investigational, all its side effects are not known. There may be rare and unknown side effects. Some of these may be life-threatening.

AEs across the 3 clinical studies performed with AEF0117 seen in 2 or more participants were headache, dizziness, gastrointestinal symptoms (dyspepsia and nausea), thermal burn, and abnormal/increased CPK.

With almost any drug, there is the possibility of having an allergic reaction. Symptoms of an allergic reaction include:

- Swelling, especially of the face and throat
- Difficulty breathing
- Itchy skin, rash, and hives
- Watery eyes
- Runny nose

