### 4 TRIAL DESIGN

#### 4.1 Overview

This is a single center, randomized, parallel-group, 2-arm, open-label, single-dose trial in healthy male and female volunteers aged 18–55 years to obtain data on the effect of food on the oral bioavailability of AEF0117.

A total of 32 healthy volunteers are planned to be enrolled. Participants will be randomized in a 1:1 ratio to receive 1 dose of AEF0117 1 mg in fasted condition (16 participants) or fed condition (16 participants). The participants will be divided into smaller cohorts of minimum 2 participants for operational reasons (adjusted to capacity of the research facility) and each cohort will include 1 fasting participant and 1 participant receiving breakfast prior to dosing.

The total trial duration for an individual participant will be up to 6 weeks (42 days) from screening (up to 28 days prior to dosing) to the final follow-up visit (14 days after dosing).

After screening, the trial includes 2 days where the participants are confined at the research facility, and thereafter 7 visits to the site (6 visits and a follow-up visit). Participants will stay in the research facility from the afternoon prior to dosing on Day 1 and until after collection of the blood sample 24 hours after dosing (i.e., Day 2) and then be discharged.

Participants will be admitted to the research facility during the afternoon on Day -1 where it will be verified that the participants are still eligible according to the inclusion and exclusion criteria,

and the baseline assessments will be performed. After an overnight stay in the research facility, participants will be randomized to fasted or fed state and dosed with a single oral dose of 1 mg AEF0117.

Blood samples for determination of AEF0117 and potential metabolites of AEF0117 in plasma will be collected before dosing and repeatedly for up to 2 weeks after dosing.

Safety will be monitored throughout the trial by assessment of AEs, suicidal risk, clinical safety laboratory parameters, pregnancy tests (females only), vital signs, ECGs, and physical examinations.

The schedule of activities summarizing all procedures is provided in section 1.3, and a description of procedures by visit is provided in section 8.1.

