### 4.2.2 Justification for dose and route

AEF0117 is formulated as a soft capsule for oral administration. In this parallel-group food-effect bioavailability trial, a single dose will be administered to each participant.

The 1 mg dose has been selected since it is considered the highest therapeutic dose and has been shown to reduce the abuse-related subjective effects of cannabis and its self-administration in a phase 2a trial. Once daily administration of 1 mg dose for 5 days in patients with CUD has shown good safety and tolerability. In healthy volunteers, multiple dosing of up to 6 mg once daily for 7 days was considered safe and well tolerated with no SAEs, and only 2 moderate and no severe TEAEs.

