#### **7.3.4.2 Intensity/severity of the adverse event**

The severity of an AE will be graded according to the scale below. The severity of the AE is determined by the principal investigator, who may consult with the sponsor’s medical monitor, if needed.

- *Mild*: A sign or symptom that do not disrupt usual activity.
- *Moderate*: A sign or symptom with sufficient intensity to affect usual activity (disturbing).

- *Severe*: A sign or symptom resulting in considerable interference with the participant's daily activities (unacceptable).

When the intensity of an AE worsens over time for a reporting period (e.g., between visits, etc.), each increase in intensity will be reported as a new AE until the event resolves.

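### The within-cohort severe-AE pause rule in 5.4.2 is met by a severe plus a milder matching AE, but not by two matching severe AEs

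*Protocol*

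**What the plan says.** Section 5.4.2 of the protocol lists the reasons for stopping, at least temporarily, the dosing of participants still to be dosed. There are three bullets.

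- **Serious AEs.** A drug-related SAE in one participant of a cohort, or two or more of the same character across cohorts.
- **Severe AEs.** Within a cohort: "Trial drug-related severe AE in 1 participant and AEs of the same character but less severe in the other participants in a dosing cohort". Across cohorts, in brackets: "severe AEs of the same character in one third of participants across at least 3 cohorts".
- **Discretion.** "Findings that, at the discretion of the investigator and/or sponsor, indicate that trial drug administration should be discontinued".

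A following paragraph covers events whose relationship to the drug is unresolved. It permits, but does not require, an interruption, and repeats the within-cohort condition: "severe AE in 1 participant and AEs of the same character but less severe in the other participants in a cohort".

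Two other sections fix how this works. Section 4.1 sets a minimum cohort of 2 and says "each cohort will include 1 fasting participant and 1 participant receiving breakfast prior to dosing". Section 7.3.4.2 states: "The severity of an AE will be graded according to the scale below". That scale has three grades (mild, moderate, severe), and severe is the highest.

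**The concern.** A pause rule should not switch off as the outcome gets worse. Here the second bullet demands that the cohort-mates' matching AEs be below the index event in severity. Since nothing ranks above severe, two severe AEs of the same character cannot satisfy it in the smallest cohort the protocol allows.

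Taken literally, the investigator must pause for one severe and one mild reaction, but has no matching stated trigger for two severe ones. In a fed/fasted pair the second pattern is the more informative: the same severe event in both food states points to the drug rather than the meal. What is at stake is the safety of the next participants to be dosed. The PK comparison is untouched.

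**Working it through.** **Inputs.** Cohort minimum of 2, one fed and one fasted (4.1). Three severity grades (7.3.4.2). 32 participants, so 16 pairs if every cohort has 2. Phase 1 exposure: 30 single-dose plus 18 multiple-dose volunteers = 48 (2.3.1). Section 2.3.1 describes their TEAEs as mild apart from 2 moderate ones, and 4.2.2 says of multiple dosing "only 2 moderate and no severe TEAEs". The severe rate *s* and milder matching rate *m* below are assumptions; the protocol gives neither.

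**1. The within-cohort limb, read literally.** One participant is severe and every other participant has a same-character AE graded below severe.

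| Cohort of 2 | As written | With same or lesser severity |
|---|---|---|
| severe + none | not met | not met |
| severe + mild | met | met |
| severe + moderate | met | met |
| severe + severe | **not met** | met |

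For cohorts of 2, 3 and 4, count the single-grade worsenings in one participant that turn the limb from met to not met. Each is a moderate AE becoming severe beside an already severe one. As written there are 2, 12 and 48 such steps. Under the corrected wording there are none.

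**2. Do the other triggers cover severe + severe?**

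- *Serious AEs:* only if an event is serious under 7.3.1, a different attribute from severity. A severe AE need not be serious.
- *One third across at least 3 cohorts:* take cohorts of 2, both severe AEs in cohort 1 and no more afterwards. After cohort 1 (2/2) and cohort 2 (2/4) the limb cannot apply. After cohort 3, 2/6 = 33.3%, just met. After cohort 4, 2/8 = 25%, not met on a cumulative count.
  - A pair in cohort 1 therefore allows up to 4 more participants to be dosed first; a pair in cohort 2 allows up to 2; a pair in cohort 3 allows none.
  - From cohort 4 on, the answer depends on the count. Three consecutive cohorts give 2 of 6 (met); the cumulative share is 2 of 8 or lower (not met).
  - If the severe AEs must themselves be spread over at least 3 cohorts, one pair never meets the limb.
- *Discretion:* permits a pause but is not an objective trigger.
- *Unresolved relationship:* same condition, same gap.

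**3. How often could it arise?** With independent participants and the same rate in both conditions, P(at least one severe + severe pair in 16) = 1 − (1 − s²)^16.

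| s | P |
|---|---|
| 2% | 0.6% |
| 5% | 3.9% |
| 6.05% | 5.7% |
| 10% | 14.9% |

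The 6.05% is the one-sided 95% upper bound for 0 of 48: 1 − 0.05^(1/48) = 0.0605.

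**4. What would the correction cost in extra pauses?** For 16 pairs, the chance that the within-cohort limb fires is 1 − (1 − 2sm)^16 as written and 1 − (1 − 2sm − s²)^16 as corrected. With m = 20%:

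- s = 2%: 1 − 0.992^16 = 12.1%, rising to 1 − 0.9916^16 = 12.6%.
- s = 5%: 1 − 0.98^16 = 27.6%, rising to 1 − 0.9775^16 = 30.5%.

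For 8 cohorts of 4, with all three others needing a matching AE, s = 2% and m = 20%: 1 − (1 − 4sm³)^8 = 0.51%, rising to 1 − (1 − [(s + m)⁴ − m⁴])^8 = 0.59%.

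**The case against.** The strongest reply is that the bullet describes a floor: one severe related AE, corroborated in the cohort-mates. A matching severe AE corroborates more strongly, so a sensible reader applies the rule all the more. The discretionary bullet sits in the same list and plainly fits two related severe AEs in a cohort of 2. Some severe AEs will also be serious, and sections 5.3.3 and 5.4.4 give further judgement-based ways to withhold dosing or end the trial. All of this stands as mitigation. The 4 extra participants would be dosed only if investigator and sponsor both declined to act, and only with cohorts of exactly 2. None of it makes the written trigger right: the section sets out objective conditions alongside discretion, and those should include the worse case.

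The probabilities also err on the high side. They treat any two severe AEs as matching, whereas the rule needs the same character and a drug relationship. The 0-of-48 bound pools single doses of 0.2 to 6 mg with 7-day dosing up to 6 mg, while this trial gives one 1 mg dose. That stands too, and strengthens the view that the case is rare.

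Finally, the corrected wording still asks for a matching AE in the other participants. If that means all of them, three severe AEs and one unaffected person in a cohort of 4 would not meet it. This is true, but it is a separate choice about how many must be affected. Once the wording is corrected, no worsening of anyone's severity turns the trigger off.

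**Conclusion.** The concern holds. As written, the within-cohort trigger in 5.4.2 fires on severe plus milder and not on severe plus severe, and no other objective limb reliably closes the gap before a third cohort. This follows from the wording and the three-grade scale and depends on no assumed rate.

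It is a minor to moderate drafting error in a safety rule, worth correcting. Practical risk is limited by the discretionary bullet, by the likelihood that staff would pause anyway, and by rarity: 0.6% to 3.9% for severe rates of 2% to 5%, under independence, equal rates in both conditions and 16 pairs. The PK objective is not affected.

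**What to change.** In the second bullet of 5.4.2, drop the requirement that the other participants' AEs be less severe and ask for AEs *of the same character, of the same or lesser severity*. Make the identical change in the unresolved-relationship paragraph. As an optional clarification, state over which cohorts the one third is counted (cumulative or a run of three).

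The edit is a few words in two places of one section and needs no extra data, visits or participants. It requires a protocol amendment; under 10.3.1 the sponsor must decide whether it is substantial, which would mean IRB/EC and regulatory approval before participants are enrolled under it. The operational downside is the small rise in the chance of a temporary pause worked out above, and in pairs the added pauses are exactly the severe-plus-severe cases that ought to pause.

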#### 7.3.4.4 Adverse event causality

The investigator must assess the relationship between the trial intervention and each occurrence of each AE using clinical judgment. The relationship or association of the AE to the trial drug will be characterized as related or not related by the investigator using the following classification:

- *Related*: The temporal relationship of the AE with the trial drug makes causality probable or possible and the AE cannot be due to another cause such as other drugs, a surgical intervention, or an underlying disease.
- *Not related*: The temporal relationship of the AE with the trial drug makes causality unlikely or certainly not related and/or the AE can be due to another cause such as other drugs, a surgical intervention, or an underlying disease.

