### 9.7.2 Adverse events

An AE with onset after administration of trial drug is considered treatment emergent.

AEs will be summarized by MedDRA SOC and PT. AE summary tables will include the number of participants reporting an AE (n), the percentage of participants with an AE (%), and the number of events reported (E). AEs will be presented by group (fasted/fed) and the total population.

The incidence of treatment-related AEs and not related AEs will be tabulated. If the investigator does not specify the relationship of the AE to trial drug the AE will be considered treatment related. AEs will also be summarized by severity (mild, moderate, severe). If the severity is missing, the AE will be regarded as severe. An AE that increases in severity over time will for the purpose of analysis be considered as one AE with the maximum intensity recorded.

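### When the causality of an SAE is still unresolved, section 5.4.2 makes the dosing hold optional, so the next cohort may be dosed in the meantime

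*Protocol*

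**What the plan says.** The relevant wording is in Protocol section 5.4.2 (Treatment discontinuation), which governs participants not yet dosed when an event occurs in a sequentially dosed cohort.

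- **Events judged drug-related.** Dosing *should* be stopped, at least temporarily, "until a thorough evaluation of safety and relationship to trial drug has been performed". The first trigger begins "Trial drug-related SAE in 1 participant in a cohort"; the second concerns drug-related severe AEs accompanied by similar, milder events.
- **Discretionary trigger in the same list.** "Findings that, at the discretion of the investigator and/or sponsor, indicate that trial drug administration should be discontinued". It carries no causality qualifier.
- **Events with causality open.** A separate paragraph begins "In case of unresolved relationship to trial drug for SAEs or severe AE in 1 participant" and gives the consequence as "the trial may be temporarily interrupted/further dosing postponed".
- **Approval.** "The investigator must obtain approval from the sponsor medical monitor before restarting dosing of the next cohort". Before an interruption, consulting the medical monitor is only recommended.

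Elsewhere, section 7.3.6 requires an SAE report within 24 hours that includes a causality assessment. Section 7.3.4.4 classifies causality as related or not related. Section 9.7.2 states how missing causality is tabulated.

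**The concern.** The pause has two stated purposes: to evaluate safety and to evaluate relationship to trial drug. When relationship has not been settled, both evaluations are outstanding, yet this is the case in which the hold is optional. A site that dosed the next cohort with an SAE's causality open would have broken no rule.

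Participants are healthy volunteers who are told to expect no immediate benefit (section 2.3.2), so a pausing rule should lean towards caution. Section 4.2.1 describes a long elimination half-life, so exposure cannot be withdrawn once the capsule is taken. The issue is participant protection; the sample size and the primary PK analysis are not affected.

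**Working it through.** No figure in the plan bears on this point, so the check is textual: does any sentence oblige the site to hold the next cohort while an SAE's relationship to trial drug is unresolved?

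1. **First trigger, 5.4.2.** It requires an SAE already called drug-related. An unresolved SAE does not meet it.
2. **Second trigger, 5.4.2.** It concerns severe AEs called drug-related. The parenthesis on one third of participants does not repeat that qualifier, but the natural reading is that it applies. In any case it concerns a pattern of severe AEs, not a single unresolved SAE.
3. **Third trigger, 5.4.2.** "Findings that, at the discretion of the investigator and/or sponsor, indicate that trial drug administration should be discontinued". An unresolved SAE can be stopped under this item. It permits a hold and does not require one.
4. **Paragraph on unresolved relationship, 5.4.2.** This is the paragraph written for the case, and its verb is *may*.
5. **Approval sentence, 5.4.2.** "The investigator must obtain approval from the sponsor medical monitor before restarting dosing of the next cohort". Restarting presupposes a stop. If the option in step 4 is not used, nothing is restarted and the sentence does not apply.
6. **Consultation sentence, 5.4.2.** Consultation is recommended before interrupting. None is required before continuing.
7. **Section 5.4.4 (Trial termination).** It lists conditions that may warrant ending the trial, after consultation. It sets no interim hold.
8. **Section 7.3.6 (SAE reporting).** The 24-hour report with a causality assessment is a reporting duty. The same section lets the investigator revise the opinion on follow-up, so the first assessment need not be final.
9. **Section 9.7.2 (Adverse events).** "If the investigator does not specify the relationship of the AE to trial drug the AE will be considered treatment related". This is a cautious default, but it governs tables at the end of the trial and holds no dosing.

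Side by side:

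| Status of the SAE | Action in 5.4.2 | Strength |
|---|---|---|
| Judged drug-related | Stop until safety and relationship are evaluated | *should* |
| Relationship unresolved | Interrupt or postpone | *may* |
| Any finding | Stop if investigator or sponsor so decides | discretionary |
| Restart after a stop | Medical monitor approval | *must* |

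No step yields an obligation to hold for the second row. The contrast is *should* against *may*, since the stronger tier is not itself worded as a *must*.

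The paragraph on unresolved relationship is loosely drafted: it is not certain whether a lone SAE qualifies, or only one accompanied by similar events in other cohort members. I read it as covering a lone SAE. On the narrower reading, a lone unresolved SAE would be left to the third trigger alone, which is also discretionary, so the result is the same.

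**The case against.** The best defence is that this is a graded rule, chosen deliberately. It names the unresolved case, offers an action, recommends consultation and places restart under the medical monitor. A firmer response to events called drug-related than to undetermined ones is defensible. The unresolved window should also be short: causality is due with the 24-hour report, and either investigator or sponsor can stop dosing on their own judgement. Cohorts exist for operational reasons, not dose escalation, and the single 1 mg dose is well below the 6 mg once daily for 7 days already given to healthy volunteers without SAEs.

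Most of this stands as a limit on likelihood. It does not supply the missing hold: each safeguard depends on someone choosing to go beyond what the rule asks.

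The objection also disposes of several stronger inferences that a reader might draw:

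- **That an SAE classed as not related escapes the section altogether.** Under 7.3.4.4 that class includes an event where the temporal relationship "makes causality unlikely or certainly not related and/or the AE can be due to another cause", so an SAE with an unconfirmed alternative cause could be placed there. The third trigger has no causality qualifier, however, and can still stop dosing.
- **That the pause exists only to settle causality, so the two tiers are the wrong way round.** The stated purpose covers safety as well as relationship. Pausing after an event already called drug-related makes sense on that ground.
- **That cohort size or the one-third pattern measures the risk.** They do not. They describe how many people are dosed together and when a different trigger applies.

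**Conclusion.** The point holds as a weakness in a stated pausing rule. Under section 5.4.2 the next cohort, at least two participants, could be dosed in compliance while the causality of an SAE is open. That number is only the minimum cohort size; the document gives no basis for a probability.

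The likelihood is low. For harm to follow from the wording, an SAE would have to occur, its causality would have to be open when a cohort was due, and both investigator and sponsor would have to choose to continue. The completed studies reported no SAEs (sections 2.1 and 2.3.1).

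The documents do not support calling this a contradiction or a known hazard. The conclusion rests on reading *may* as permissive and *restarting* in its ordinary sense. A generous reader could extend the approval requirement to every next cohort, but the text does not say so. The change is worth making because it costs little and protects people who gain nothing from taking part.

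**What to change.** In the unresolved-relationship paragraph of section 5.4.2, replace the optional clause with:

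*the trial may be temporarily interrupted, and dosing of the next cohort should be postponed until the investigator and the sponsor medical monitor have assessed safety and the relationship to trial drug*

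This keeps the option to interrupt the whole trial and gives the next cohort the same *should* as events judged drug-related. Leave the consultation and restart-approval sentences as they are.

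Two further edits might suggest themselves and are better avoided. Deeming an SAE unresolved whatever its recorded classification under 7.3.4.4 would create a second causality standard beside the one used for reporting. Adding a drug-related qualifier to the parenthesis in the second trigger could narrow a safety trigger.

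The cost is one replaced clause, a possible short delay to a cohort, and repeat screening for anyone whose Day -28 to Day -2 window lapses during the delay.
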